2.2.1.2 Secondary efficacy endpoint(s)

All time to event endpoints are measured from date of randomization. It is expected that there will be approximately 24 hours between randomization and dosing.

All endpoints associated with each secondary objective are listed together. The key endpoints are written in bold to be analysed/summarized at the second interim analysis when all participants have had the opportunity to complete Day 28 Procedures. Collected endpoints and their timing that may be used to derive the endpoints are listed in the third column. Alternative sources of the same information may be available and used.

There is overlap on some of the measurements across endpoints. Some may be taken once for each endpoint or taken once and used for more than one endpoint.

Details of the items in the 6-point ordinal score are provided below this table. Brief details of SOFA, are provided and further information can be obtained from the hyperlink.

Secondary Objective	Endpoint	Measurement

1) To study if early intervention with Zilucoplan® affects clinical outcome defined by duration of hospital stay, 6-point ordinal scale, time to defervescence, supplemental oxygen use, SOFA score
	
Incidents of participants reporting each severity rating in 6-point ordinal scale at D1, D6, D15 and D28
 
Change from baseline in 6-point ordinal scale to Day 6, Day 15 and Day 28 (by phone call) weeks post randomisation
 
Time to at least a 2-point improvement or discharge sustained up to D28 on the 6-point ordinal scale during 28-day assessment period
 
Percentage of participants reporting at least a 2-point improvement sustained to D28 or discharge
 
AUEC/Time using the 6-point score recorded daily – up to D15, D28 and all data recorded
 
Percentage of participants who record a 2-point improvement from baseline or discharge at D6, D15 and D28
 
Percentage of participants not deteriorating according to the ordinal scale by 1 or 2 points on D6, D15 and D28
 
6-point ordinal Scale at D6 and D15 and D28 in relation to D-Dimers and complement C5a levels at baseline
	
6-point ordinal scale measured daily up to discharge, D28 and follow-up
 
Lab values at baseline for D-Dimers and C5a

	
Change from baseline in SOFA score (https://www.mdcalc.com/sequential-organ-failure-assessment-sofa-score) to Day 6, Day 15 (or at discharge, whichever comes first)
	
SOFA score measured at D1, D6 and D15

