
Objective 2
 
Change from baseline in 6-point ordinal scale to Day 6, Day 15 and Day 28
	
Change from baseline at each relative day for each participant. If a participant has died (score=1) or discharged from hospital (score=6), these values will carry forward onto subsequent days. For participants who are missing values after any day for any other reason, the value will remain missing. For participants who miss some intermediate values, the latest value prior to the missing value will be carried forward until the day where data are recorded again.
 
The additional scores derived for the previous endpoint will not be used in change from baseline
 
(One line per day per participant dataset)
	
Summary table providing n, mean change from baseline, SD change from baseline, median, minimum and maximum on each specified nominal day by treatment arm
 
Graph of change from baseline over time for each participant by treatment, and the average lines for each treatment.
 
For final analysis: MMRM fitting response variable change from baseline against fixed effects for specified nominal days, treatment and treatment*nominal day interaction. Baseline score as covariate and baseline score*nominal day as additional terms. Participant as random effect.

Objective 2
 
Time to at least a 2-point improvement or discharge sustained up to (D15 for interim analysis 1) D28 on the 6-point ordinal scale during 28-day assessment period (=Response)
 
Note: for both the interim analyses and final analyses up to D15 and D28 respectively, if the 2-point change occurred on D15 or D28, and the
	
Create TTE dataset for cumulative response rate analysis with 2 variables each for analysis up to D15 and up to D28 with one line per participant providing time to response and censor status. Censor status=0 for patients with response and =1 on relative day for: patients who have: withdrawn from treatment and/or study; discharged from first hospital for reasons other than improvement; have no response by analysis date (censor=1 at analysis
	
Kaplan-Meier analysis using PROC LIFETEST. Strata ACTARM.
 
Request Failure plot adjusting axis and heading titles to reflect responder and not failure
 
Output statistics:
 
Appropriate statistics from analysis as indicated in mock shell

Endpoint	Derivation	Analysis

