
patient remained in hospital, the patient will be classified as a responder, even though the 2-point change had not been ‘sustained’.
	
date). If Time to Response >15 and censor=1 for analysis up to D15, Time to Response=15. If Time to Response >28 and censor=1 for analysis up to D28, Time to Response=28. For patients who have died Time to Response is set to D15 or D28 respectively and censored at this time. Note: Treatment will be merged into the TTE dataset. In addition to other variables that may be used as covariates in final analysis.
 
(one line per participant dataset)
	

Objective 2 Percentage of participants reporting at least a 2-point improvement sustained to D28 or discharge
	
Use D28 response indicator variable defined above
	
PROC FREQ/PROC LOGISTIC(if covariates are added) Model: Response=ACTARM +covariates (if added) Output percentage response on each treatment. Odds ratio and 95% confidence interval

Objective 2 AUEC/Time using the 6-point score recorded daily – up to D15, D28 and all data recorded
	
For each participant calculate the area under the curve and divide by 15 for up to D15 and by 28 for up to D28 (higher average score per day the better the response). Use last value brought forward for any missing values until next data entry. For discharge, carry forward score=6 for each day post discharge day. For death, carry forward score=1 for each day post death day.
	
Analyse AUEC/Time using analysis of variance with ACTARM as a two-level factor and baseline score as a covariate

Endpoint	Derivation	Analysis

Objective 2 Percentage of participants who record at least 2-point improvement from baseline or discharge (response) between D1-D6, D7-D15 and D16-D28
	
Responder classified as above. Create indicator variable (3 levels) if the relative day of START of response is between D1 and D6, between D7 and D15 or between D16 and D28. Each responder participant can only be within one of these categories. Participants who have a missing value are classified as non-responders
	
Frequency table and percentage responders in each of the categories defined by the indicator variable, by treatment. Exact 95% confidence intervals for each percentage

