
Objective 2 Percentage of participants not deteriorating according to the ordinal scale by 1 point between D1 and D6, between D7 and D15 and between D16 and D28 – not deteriorating corresponds to Stable + Responders
	
A participant is classified as Stable + Response if at no time CFB < -1. Create indicator variable (3 levels) if the relative day of START of Stable or Response falls between D1 and D6, between D7 and D15 and between D16 and D28 for each participant
	
Frequency table and percentage responders in each of the categories defined by the indicator variable, by treatment. Exact 95% confidence intervals for each percentage

Objective 2 6-point ordinal Scale at D6 and D15 and D28 in relation to D-Dimers and complement C5a levels at baseline
		
Box-whisker plot of baseline D-Dimers and complement C5a for each score (x-axis) reported on each of D6, D15 and D28

Objective 2 Change from baseline in SOFA score (https://www.mdcalc.com/sequential-organ-failure-assessment-sofa-score)
	
Change from baseline to D6 and D15 in SOFA score
	
Summary statistics for raw data and change from baseline

Endpoint	Derivation	Analysis
to Day 6, Day 15 (or at discharge, whichever comes first)		

Objective 2
 
Number of days with fever (defined as 37.1°C or more) during 28-day assessment period
	
Create indicator variable for each participant on each day where temperature is above 37.1 °C
 
Create variable with total number of days where temperature was above 37.1 °C for each participant
 
Create variable for each participant giving total number of days where temperature was recorded
	
Summary statistics to provide n, average number of days, SD, median, minimum and maximum where temperature was above 37.1 °C by treatment
 
Produce line plot of temperature over time for each patient together with average line per treatment group.
 
Temperatures are due to be taken daily until discharge – indicate the number of subjects on each day in each treatment arm

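### Table 8.1 tabulates when a sustained response began, so its Day 7–15 and Day 16–28 percentages do not estimate the listed endpoint of response at Day 15 and Day 28

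*SAP*

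**What the plan says.** SAP 2.2.1.2 lists the endpoint as "Percentage of participants who record a 2-point improvement from baseline or discharge at D6, D15 and D28". Protocol 4.3 lists it among the exploratory endpoints in identical words. Both describe a participant's state on three named days.

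Table 8.1 in SAP 8.2 relabels the endpoint with the period "between D1-D6, D7-D15 and D16-D28". The derivation column reads "Create indicator variable (3 levels) if the relative day of START of response is between D1 and D6, between D7 and D15", with Day 16 to Day 28 as the third level, and adds "Each responder participant can only be within one of these categories". It opens with "Responder classified as above"; the rows above that define a responder require the improvement to be sustained. Missing values count as non-response. The output is "Frequency table and percentage responders in each of the categories defined by the indicator variable, by treatment", with an exact 95% confidence interval for each percentage. The denominator is not stated.

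The next row, on not deteriorating, uses the same device: a participant is classified by "if the relative day of START of Stable or Response falls between D1 and D6, between D7 and D15 and between D16 and D28". To qualify, the change from baseline must never fall below −1. SAP 2.2.1.2 lists this endpoint too by status on Day 6, Day 15 and Day 28.

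**The concern.** A percentage in response at Day 15 should count everyone who is improved or home on that day, whenever that began. A table of onset intervals counts only those whose response began after Day 6. Early responders are removed from the later rows, so a high early response leaves fewer participants available to appear there.

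The trial's hypothesis is that the drug improves oxygenation and recovery. If it brings recovery forward, the later rows may show a smaller percentage on zilucoplan even though more participants on that arm have responded by each day. SAP 3.1 makes 95% confidence limits, without p-values, the inferential output for secondary endpoints. A table whose intervals belong to a different quantity can therefore be misread. SAP 4.4.2 also places endpoints based on the 2-point improvement in the second interim analysis, which may serve as final for key secondary endpoints and guide further research.

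**Working it through.** **No plan figure to reproduce.** The documents give no expected response rate for this endpoint; the sample size calculation concerns PaO₂/FiO₂ only. All rates below are assumptions. Only the arm sizes, 54 and 27, come from the plan (SAP 2.4).

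**What each version measures.** Let F(t) be the proportion of an arm whose response has begun by Day t.

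- Onset rows as in Table 8.1: F(6), F(15) − F(6), F(28) − F(15).
- Cumulative response: F(6), F(15), F(28).

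The between-arm difference in the Day 7–15 row equals the lead at Day 15 minus the lead at Day 6. In the Day 16–28 row it equals the lead at Day 28 minus the lead at Day 15. A later row is thus lower in the faster arm exactly when that arm's lead narrows over the interval. If both arms have equal response by Day 28, an arm ahead at Day 15 must be lower in the last row, and an arm ahead at Day 6 must be lower over the two later rows together.

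**Example 1: same response by Day 28, A sooner.** Assumed onsets are A 28, 12, 4 of 54 and B 8, 8, 6 of 27.

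| | Onset rows (%) | Cumulative D6 / D15 / D28 (%) |
|---|---|---|
| A | 51.9 / 22.2 / 7.4 | 51.9 / 74.1 / 81.5 |
| B | 29.6 / 29.6 / 22.2 | 29.6 / 59.3 / 81.5 |

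The lead goes from 22.2 to 14.8 to 0 points, so the later rows differ by −7.4 and −14.8 points although A is never behind.

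**Example 2: A sooner and higher overall.** Assumed onsets are A 22, 16, 8 of 54 and B 7, 7, 4 of 27. Onset rows are A 40.7 / 29.6 / 14.8% and B 25.9 / 25.9 / 14.8%. A is not lower in any row.

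**The denominator changes the picture.** If percentages are taken of responders, Example 2 becomes A 47.8 / 34.8 / 17.4% (of 46) and B 38.9 / 38.9 / 22.2% (of 18). A is now lower in both later rows, although by Day 28 it has 85.2% response (46/54) against 66.7% (18/27).

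**Range over control recovery times.** Take F(t) = 1 − exp(−λt), with λ = ln 2 / median in control and 1.5 times that in the faster arm, over arm N. For a control median of 7 days, λ = 0.0990 and 0.1485, so F(6) = 44.8% and 59.0%.

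| Control median (days) | Control rows (%) | Faster-arm rows (%) | Faster arm lower in | Cumulative by D15, control vs faster (%) |
|---|---|---|---|---|
| 7 | 44.8 / 32.6 / 16.4 | 59.0 / 30.2 / 9.2 | both later rows | 77.4 vs 89.2 |
| 10 | 34.0 / 30.6 / 21.0 | 46.4 / 32.6 / 15.6 | D16–28 only | 64.6 vs 79.0 |
| 14 | 25.7 / 26.7 / 22.6 | 36.0 / 31.2 / 20.3 | D16–28 only | 52.4 vs 67.2 |
| 28 | 13.8 / 17.2 / 19.0 | 20.0 / 22.7 / 21.9 | neither | 31.0 vs 42.7 |

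The cumulative percentages favour the faster arm in every line.

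**Summing the rows is not a full repair.** Because the responder definition requires a sustained improvement, someone improved on Day 6 who later loses the improvement appears in no row, yet is improved at Day 6 under SAP 2.2.1.2. The separate confidence intervals cannot be added either.

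**Consistency within the SAP.** Elsewhere discharge is carried forward. The ordinal-category row keeps discharged participants in numerator and denominator on later days, the change-from-baseline row carries score 6 forward, and SAP 3.2.1.3 maps a Day 4 discharge to Days 6, 15 and 28 for the primary endpoints.

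**Not deteriorating.** The start of stability is not defined. At baseline, mapped to Day 1, the change is 0, which already meets the rule. On the natural reading, then, nearly everyone who qualifies starts on Day 1 and falls in Day 1–6, leaving the later rows almost empty. Separately, the row is labelled as not deteriorating by 1 point, but scores are whole numbers and a 1-point decline gives −1, which is not below −1. Such a participant passes.

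**The case against.** The strongest reply has four parts.

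- **The rows are openly labelled as intervals.** No row claims to be status at Day 15 or Day 28, and no between-arm difference or test is planned for this row. This is true, but the row is the only analysis given for the endpoint listed in SAP 2.2.1.2, and it answers a different question.
- **Related information is planned elsewhere.** Table 8.1 includes a Kaplan-Meier analysis ("Create TTE dataset for cumulative response rate analysis"), a Day 28 responder percentage with odds ratio, and counts per ordinal category at Days 6, 15 and 28. SAP 4.4.1 allows a comparison of response sustained to Day 15 at the first interim. This substantially limits the harm. But the Kaplan-Meier analysis censors withdrawals, the Day 28 row covers one day, and the interim comparison is optional and made at about half enrolment. No other Table 8.1 row gives the binary percentage at Day 6 and Day 15 with missing as non-response.
- **The stakes are low.** Protocol 4.3 makes the endpoint exploratory, and SAP 4.5 says findings need confirmation. This stands.
- **The reading of stability as starting on Day 1 is inferred.** This also stands, but the SAP offers no other definition.

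A reader might infer two stronger claims. One is that the later rows necessarily reverse when the drug speeds recovery; Example 2 and the 28-day line show that they need not. The other is that this is a change from the protocol that SAP 3.8 should have declared. SAP 1 bases the plan on Protocol 3.0, which is not available, and the protocol's change log says the secondary endpoints were later updated to follow the SAP. An undeclared departure cannot be shown.

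**Conclusion.** The mismatch is between SAP 2.2.1.2 and Protocol 4.3 on one side and Table 8.1 on the other, and it rests on the text alone. The Day 7–15 and Day 16–28 percentages and their intervals measure new sustained responses, not response at Day 15 and Day 28.

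How misleading this is depends on rates the documents do not give. With arm N as denominator and the assumed rate ratio of 1.5, the faster arm ranges from lower in both later rows (control median 7 days) to lower in neither (28 days). Similar Day 28 response in both arms makes a lower later row most likely. The calculations treat each response as lasting once begun and do not model deaths or withdrawals.

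The non-deterioration row has the same flaw, an undefined start, and a threshold one point looser than its label. The point is worth correcting, but its impact is modest and it does not touch the primary analysis.

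**What to change.** In Table 8.1, replace the 3-level variable with three separate yes/no variables per participant, at nominal Day 6, Day 15 and Day 28. Each is yes if the participant is at least 2 points better than baseline or has been discharged for improvement, with discharge carried forward and death and missing counted as non-response. State that the denominator is all participants in the arm, and report the percentage with its exact 95% confidence interval by arm. Say explicitly that sustained response is not required here, since SAP 2.2.1.2 does not ask for it. Keep the onset-interval table, if wanted, only as a description of timing, labelled as such and with its denominator stated.

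For not deteriorating, classify status at Day 6, Day 15 and Day 28 as SAP 2.2.1.2 lists it, and set the change-from-baseline threshold to match the label: −1 or lower counts as deterioration by 1 point, and −2 or lower as deterioration by 2 points.

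The cost is SAP wording and a small programming change, with no new data. It should be done before database lock, because SAP 3.8 rules out amending the SAP for later changes.

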6.2. Exclusion Criteria

- Patients with known history of serious allergic reactions, including anaphylaxis, to Zilucoplan® or inability to receive antibiotic prophylaxis due to allergy to ALL of the antibiotics that can be given for prophylaxis of meningococcal disease
- History of active or past meningococcal disease
- Invasive mechanical ventilation > 24 h at randomization**
- Patient on ECMO at screening
- Clinical frailty scale above 3 before onset of the COVID-19 episode
- Weight below 54 kg as measured max 1 week prior to inclusion
- Weight above 150 kg as measured max 1 week prior to inclusion
- Active bacterial or fungal infection
- Unlikely to survive beyond 48h
- Neutrophil count below 1500 cells/microliter
- Platelets below 50.000/microliter
- Patients enrolled in another investigational drug study
- Patients on high dose systemic steroids (> 8 mg methylprednisolone or equivalent for more than 1 month) or other moderately immunosuppressive drugs (in the opinion of the investigator) for COVID-19 unrelated disorder
- Patients on current complement inhibiting drugs
- Serum transaminase levels >5 times upper limit of normal, unless there are clear signs of cytokine release syndrome defined by LDH >300 IU/L and ferritin >700 ng/ml
- Pregnant or breastfeeding females (all female subjects deemed of childbearing potential by the investigator must have negative pregnancy test at screening)

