	
Time since randomization until first use of high-flow oxygen devices or non-invasive mechanical ventilation or invasive mechanical ventilation or ECMO in non-ventilated participants (i.e. excluding participants who are ventilated within 24h prior to or after randomization) during 28-day assessment period
	
Use Vital Parameter CRF,

	
Time since randomization to progression to ARDS
	
Randomisation date
 
Date of ARDS diagnosis

	
Duration of ICU stay in participants that enrolled in trial that were on invasive or non-invasive mechanical ventilation or high-flow oxygen devices within 24h prior to or after randomization during 28-day assessment period
 
Duration of ICU stay in participants that enrolled in trial that were on invasive or non-invasive mechanical ventilation for less than 24h prior to or after randomization during 28-day assessment period
	
Use DATES and Vital Signs dataset

Secondary Objective	Endpoint	Measurement

3) To study if treatment with Zilucoplan® affects all-cause mortality rate at day 28 and at 12-22 weeks post-randomisation
	
All-cause mortality rate at 28 days post randomisation (all treated participants)
 
All-cause mortality rate at 28 days post randomisation (excluding participants that required invasive mechanical ventilation or ECMO, non-invasive mechanical ventilation or high-flow oxygen devices within 24 hours prior to or after randomisation)
 
All-cause mortality rate at 28 days post randomisation (excluding participants that required invasive mechanical ventilation or ECMO within 24 hours prior to or after randomisation)
 
All-cause mortality rate at 28 days post randomisation (excluding participants that required invasive mechanical ventilation or ECMO, non-invasive mechanical ventilation or high-flow oxygen devices within 24 hours prior to or after randomisation)
 
All-cause mortality rate at 28 days post randomisation (only including participants that required invasive mechanical ventilation or ECMO within 24 hours prior to or after randomisation)
 
All-cause mortality at follow up 12-22 weeks post-randomisation for all treated participants
	
6-point ordinal scores, DATES and VITAL SIGNS datasets

Secondary Objective	Endpoint	Measurement

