4 STATISTICAL/ANALYTICAL ISSUES

4.1 Adjustments for covariates

Covariates such as sex, age, BMI (measure of obesity) and race may also be included in the models if by the time of analysis these have been identified as key differentiators in terms of COVID-19 recovery.

Weight may also be used (independently of BMI) as a covariate to explore the impact of weight on results as the usual dosing regimen for Zilucoplan® is to dose by weight.

In addition, the impact on the results of disease severity at baseline may be explored using the 4 middle categories of the 6 point ordinal scale to define disease severity at baseline as a covariate

Where indicated, some secondary endpoints will explore the impact of baseline laboratory values on efficacy endpoints eg Baseline D-Dimers and C5a values.

The addition of the interaction of any baseline covariate with treatment may be explored to identify any evidence to suggest a differential impact on results.

Prior to fitting any model, all data will be explored graphically.

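### The row for not deteriorating by 1 point in SAP Table 8.1 uses a strict cut-off that passes every one-point fall, including death from baseline score 2

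*SAP*

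**What the plan says.** The endpoint column of SAP Table 8.1 (Objective 2) has the label "Percentage of participants not deteriorating according to the ordinal scale by 1 point between D1 and D6", continued for two later intervals, and equates not deteriorating with being stable or a responder. The derivation column then gives the operative rule: "A participant is classified as Stable + Response if at no time CFB < -1". The output is a frequency table with exact 95% confidence intervals by arm.

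The endpoint list in SAP 2.2.1.2 words it differently: "Percentage of participants not deteriorating according to the ordinal scale by 1 or 2 points on D6, D15 and D28". Protocol 4.3 has the same wording and classes the endpoint as exploratory.

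Two other rows of Table 8.1 bear on deaths. The change-from-baseline row states: "If a participant has died (score=1) or discharged from hospital (score=6), these values will carry forward onto subsequent days". The time-to-response row has a rule of its own: "For patients who have died Time to Response is set to D15 or D28 respectively and censored at this time". The non-deterioration row has no separate death rule.

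**The concern.** The label and the derivation describe different endpoints. Under the label, a one-point fall is deterioration. Under the rule it is Stable + Response, although a participant whose worst change is −1 and who never improves is neither stable nor a responder.

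The mismatch is most serious at the lower end of the scale. A fall from 3 to 2 is a move to invasive ventilation or ECMO, and a fall from 2 to 1 is death. Both have a change of −1 and pass as non-deterioration. Limiting progression is the trial's stated justification (Protocol 3.1 and 5.1), and this is the ordinal-scale endpoint named for it. Programmed as written, the table would not show what its title says.

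**Working it through.** **Inputs**
- Scale: integers 1 to 6, 1 = death, 2 = hospitalised on invasive ventilation or ECMO, 6 = not hospitalised (SAP 2.2.1.2). Higher is better, so a negative change is worsening.
- Death enters as score 1 and is carried forward (SAP Table 8.1, change-from-baseline row).
- Possible baseline scores: 2 to 5. SAP 4.1 describes "using the 4 middle categories of the 6 point ordinal scale to define disease severity at baseline as a covariate".
- Baseline 2 is eligible. Protocol 6.2 excludes "Invasive mechanical ventilation > 24 h at randomization" and patients on ECMO at screening, but not shorter invasive ventilation. The SAP also plans a 28-day mortality analysis "only including participants that required invasive mechanical ventilation or ECMO within 24 hours prior to or after randomisation".
- Planned arm sizes: 54 and 27 (SAP 2.4).

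The plan states no figure to reproduce here. The check is a full enumeration.

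**Formula.** CFB = worst score − baseline score. The rule as written flags deterioration if CFB < −1. A literal 1-point rule flags it if CFB ≤ −1. A 2-point rule with deaths counted flags it if CFB ≤ −2 or the participant died.

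| Baseline | Worst | CFB | As written | 1-point | 2-point or death |
|---|---|---|---|---|---|
| 2 | 1 (death) | −1 | no | yes | yes |
| 3 | 2 | −1 | no | yes | no |
| 3 | 1 (death) | −2 | yes | yes | yes |
| 4 | 3 | −1 | no | yes | no |
| 4 | 2 | −2 | yes | yes | yes |
| 4 | 1 (death) | −3 | yes | yes | yes |
| 5 | 4 | −1 | no | yes | no |
| 5 | 3 | −2 | yes | yes | yes |
| 5 | 2 | −3 | yes | yes | yes |
| 5 | 1 (death) | −4 | yes | yes | yes |

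**Results**
- Worsening outcomes: 1 + 2 + 3 + 4 = 10. The rule as written flags 0 of 1, 1 of 2, 2 of 3 and 3 of 4 from baselines 2, 3, 4 and 5, so 6 of 10. The literal 1-point rule flags 10 of 10. The 2-point rule with deaths flags 7 of 10.
- From baseline 2 the lowest possible CFB is 1 − 2 = −1, which is not below −1. No such participant can be flagged. Death is flagged from baselines 3, 4 and 5 only.
- The four no-change outcomes are treated alike by all the rules.
- Effect per reclassified participant on the arm's overall percentage: 100/54 = 1.85 points in Arm A and 100/27 = 3.70 points in Arm B. With the interval variable left as it is, correcting the 1-point row can only lower that percentage or leave it unchanged.

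These are counts of outcome types, not probabilities.

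**The case against.** The strongest reply is that a 2-point threshold was intended, mirroring the 2-point response definition, and that the label is loosely drafted. The fever row nearby has a similar slip: the endpoint includes 37.1 °C and the derivation takes only values above it. This reading does not rescue the row. The label would then be wrong, the 1-point half of the listed endpoint would be missing, and death from baseline 2 would still count as stable. A sign lost in reading the PDF is unlikely, since ≤ and ≥ survive elsewhere in the SAP.

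A second reply is that little depends on it. This largely stands. The endpoint is exploratory in the protocol, SAP 3.1 gives no p-values for secondary objectives, and deaths and daily score distributions are tabulated elsewhere. One gap remains: time to first use of ventilatory support excludes participants ventilated around randomisation, so intubation of someone on non-invasive ventilation at baseline is not an event there.

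Third, threshold and timing act together. The endpoint lists refer to D6, D15 and D28, whereas Table 8.1 uses intervals, an at-no-time condition and an undefined start of stability. That conflict is real and should be settled in the same edit. It also means that the percentage steps above apply to the overall percentage, not to each interval's figure.

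Fourth, a tighter 1-point rule excludes a participant who dips one point and is later discharged as a responder. This is true and should be stated. The present rule already does the same for two-point dips.

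Fifth, counting a fall from 2 to 1 in a 2-point row is a choice, because it is one point on the scale. That is fair. It therefore has to be written as an explicit death rule.

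Last, the evidence for baseline score 2 is partly indirect: the covariate in SAP 4.1 is optional, and the mortality subgroup includes ventilation started up to 24 hours after randomisation. Eligibility under Protocol 6.2 is enough for the point. SAP 8.2 refers to mock shells for further detail. They are not available here, but the rule in the SAP is explicit.

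**Conclusion.** The rule does not implement its label. It passes all four one-point falls, including death from baseline 2, and flags 6 of the 10 possible worsening outcomes. This follows from the SAP's own definitions. It assumes that the row uses the change-from-baseline values defined earlier in Table 8.1, with death as score 1, and that baseline scores run from 2 to 5. The number of participants affected is unknown, because the documents give neither a baseline score distribution nor transition rates. The primary analysis is untouched. The row should be fixed before the table is programmed, but the consequence is limited to one descriptive table.

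**What to change.** In Table 8.1, keep the at-no-time condition and make three edits.

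1. For the 1-point row, classify a participant as Stable + Response only if CFB is never ≤ −1. This captures every death from baselines 2 to 5 without a further rule.
2. Add a separately labelled 2-point row, where CFB is never ≤ −2, so that both halves of the listed endpoint are reported.
3. In the 2-point row, state that any death counts as deterioration whatever the baseline score. The only participants this changes are deaths from baseline 2.

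State in the SAP that a participant who dips one point and later meets the response definition is a responder but not Stable + Response in the 1-point row. In the same revision, define when stability starts and reconcile the intervals with the D6, D15 and D28 wording in SAP 2.2.1.2 and Protocol 4.3, here and in the companion row for 2-point improvement.

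The cost is a short SAP edit and a small programming change: one threshold, one extra row and one death rule. No new data are needed.
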